**6.4.5. Week 16 and 20 ( $\pm$  3 days) – GT-3 Subjects only**

- Vital signs, including body weight and height measurements
- Perform symptom-directed physical examination
- Assessment of AEs and concomitant medications
- Obtain blood samples for
  - Hematology
  - Chemistry
  - Coagulation tests
  - HCV RNA
  - Viral sequencing (archive)
  - Single PK
- Obtain urine sample for:
  - $\beta$ -hCG pregnancy test for females of childbearing potential only
- Review medication compliance with subject and/or parent/guardian (subject should return all study drugs at these visits)
- Dispense study drugs as directed by the IWRS

**6.4.6. Week 24 ( $\pm$  3 days) – GT-3 Subjects only**

- Perform complete physical examination
- Tanner Staging Assessment
- Vital signs, including body weight and height measurements
- Assessment of AEs and concomitant medications
- Pregnancy prevention counseling including partner pregnancy prevention for male participants (Subjects 12 to < 18 years of age and subjects < 12 years of age at the discretion of the Investigator based on subject's pubertal status)

- Obtain blood samples for:
  - Hematology
  - Chemistry
  - Coagulation tests
  - HCV RNA
  - Viral sequencing (archive)
  - TSH
  - Single PK
- Obtain urine sample for:
  - $\beta$ -hCG pregnancy test for females of childbearing potential only
- Subject completes quality of life survey: Subject is to review questionnaire with a parent/guardian and write/mark answers directly onto the questionnaire
- Review medication compliance with subject and/or parent/guardian.
- GT-3 Subjects should return all bottles and kits at the Week 24 Visit

#### **6.4.7.            Unscheduled Visit/Early Termination Visit**

A subject should attend an unscheduled visit if requested by the sponsor or the investigator. The assessments are at the investigator's discretion.

The Sponsor/CRO should be informed when a subject comes off treatment due to an adverse event. If a subject discontinues treatment then the assessments outlined below should be performed.

- Perform complete physical examination
- Tanner Pubertal Stage Assessment
- Vital signs, including body weight and height measurements
- Assessment of AEs and concomitant medications
- Pregnancy prevention counseling including partner pregnancy prevention for male participants (Subjects 12 to < 18 years of age and subjects < 12 years of age at the discretion of the Investigator based on subject's pubertal status)

- Obtain blood samples for:
  - Hematology
  - Chemistry
  - Coagulation tests
  - HCV RNA
  - Viral sequencing (archive)
  - TSH
  - Single PK
- Obtain urine sample for:
  - $\beta$ -hCG pregnancy test for females of childbearing potential only
- Subject completes quality of life survey: Subject is to review questionnaire with a parent/guardian and write/mark answers directly onto the questionnaire.
- Review medication compliance with subject and/or parent/guardian.
- Subjects should return all bottles and kits at the Early Termination Visit

All subjects should complete Post-Treatment assessments after early termination, as described in Section 6.5.

## **6.5. Post-Treatment Assessments**

### **6.5.1. 4-Week Post-Treatment Visit ( $\pm$ 5 days)**

- Vital signs, including body weight and height measurements
- Perform symptom-directed physical examination
- Assessment of AEs and concomitant medications
- Obtain blood samples for:
  - Hematology
  - Chemistry

- HCV RNA
- Viral sequencing (archive)
- Obtain urine sample for:
  - $\beta$ -hCG pregnancy test for females of childbearing potential only
- Pregnancy prevention counseling including partner pregnancy prevention for male participants (Subjects 12 to < 18 years of age and subjects < 12 years of age at the discretion of the Investigator based on subject's pubertal status)

Female subjects of childbearing potential should be provided with Urine Pregnancy Test-Kits, instructed on their use and requested to continue to self-monitor for pregnancy for 6-months after their last dose of RBV. If required by local regulations, additional pregnancy tests beyond 6 months may be added. The subject should be contacted every 4 weeks and asked to report results of the urine pregnancy tests. If a positive urine pregnancy test is reported, the subject should return to the clinic for a serum pregnancy test.

#### **6.5.2. 12-Week Post-Treatment Visit ( $\pm$ 5 days)**

- Vital signs, including body weight and height measurements
- Perform symptom-directed physical examination
- Assessment of SAEs
- Perform Tanner Pubertal Stage assessment
- Obtain blood samples for
  - Hematology
  - Chemistry
  - HCV RNA
  - Viral sequencing (archive)
- Obtain urine sample for:
  - $\beta$ -hCG pregnancy test for females of childbearing potential only
- Pregnancy prevention counseling including partner pregnancy prevention for male participants (Subjects 12 to < 18 years of age and subjects < 12 years of age at the discretion of the Investigator based on subject's pubertal status)

- Subject completes quality of life survey: Subject is to review questionnaire with a parent/guardian and write/mark answers directly onto the questionnaire

### **6.5.3. 24-Week Post-Treatment Visit ( $\pm$ 5 days)**

- Vital signs, including body weight and height measurements
- Perform symptom-directed physical examination
- Assessment of SAEs
- Tanner Pubertal Stage Assessment
- A single X-ray of the left wrist, hand, and fingers for Bone Age Assessment
- Obtain blood samples for
  - HCV RNA
  - Viral sequencing (archive)
- Obtain urine sample for  $\beta$ -hCG pregnancy test for females of childbearing potential only
- Subject completes quality of life survey: Subject is to review questionnaire with a parent/guardian and write/mark answers directly onto the questionnaire.

All subjects (those who attain SVR24 or those who do not attain SVR24) who do not initiate other experimental or approved anti-HCV therapy will be followed every 6 months for assessments of growth, quality of life, and long-term viral suppression (if applicable) in a separate protocol (GS-US-334-1113). This follow-up will continue for 5 years.

## **6.6. Procedures and Specifications**

### **6.6.1. Clinical Laboratory Analytes**

Hematology: Hematocrit, Hemoglobin (Hb), Platelet count, Red blood cell count (RBC), White blood cell count (WBC) with differential (absolute and percentage) including Lymphocytes, Monocytes, Neutrophils, Eosinophils, Basophils, Reticulocyte count and MCV.

Coagulation: INR, Prothrombin time (PT), Activated partial thromboplastin time (APTT)

Chemistry: Alanine aminotransferase (ALT/SGPT), Aspartate aminotransferase (AST/SGOT), Albumin, Alkaline phosphatase, Creatinine, Total Bilirubin (reflex to Direct Bilirubin), Glucose, Lipase, Potassium, Sodium, Gamma-glutamyl transferase (GGT), alpha fetoprotein (AFP), alpha-1 anti-trypsin, creatine kinase (CK) and amylase.

Urinalysis: Appearance, Blood, Color, Glucose, Leukocyte esterase, pH, Protein, Urobilinogen. Reflex to microscopic urinalysis if dipstick result is abnormal.

Virological Tests: Serologies for HCV, HBV and HIV. HCV RNA will be measured using the COBAS® AmpliPrep/COBAS® TaqMan® HCV Test, v2.0 for Use with the High Pure System. HCV GT and subtype will be determined using the Siemens VERSANT® HCV Genotype INNO-LiPA 2.0 Assay. Gilead reserves the right to use alternate assays for HCV RNA and HCV GT should the above assays become unavailable.

IL28B genotype will be determined by polymerase chain reaction (PCR) amplification of the SNP, rs12979860, with sequence specific forward and reverse primers and allele specific fluorescently labeled TaqMan® MGB probes. Gilead reserves the right to use alternate assays for IL28B determination should the above assay become unavailable.

Pregnancy Tests: Serum  $\beta$ -hCG, Urine  $\beta$ -hCG (if positive, requires immediate confirmation with Serum  $\beta$ -hCG)

Additional Tests: Hemoglobin A1c (HbA1c), TSH (reflex Free T4), Alfa fetoprotein (AFP), Alpha-1 anti-trypsin (AAT), Urine drug screen (for amphetamines, cocaine, methadone, opiates).

#### **6.6.2. Medical History**

Medical history including details regarding illnesses and allergies, date(s) of onset, and whether condition(s) is currently ongoing, and medication history will be collected on all subjects during screening. Parental heights will be recorded at Screening.

#### **6.6.3. Complete Physical Examination**

A complete physical examination must include source documentation of general appearance, and the following body systems: Head, neck and thyroid; eyes, ears, nose, throat, mouth and tongue; chest (excluding breasts); respiratory; cardiovascular; lymph nodes, abdomen; skin, hair, nails; musculoskeletal; neurological.

#### **6.6.4. Tanner Pubertal Stage Assessment**

The Tanner Stage scale is available in [Appendix 4](#). Perform Tanner Pubertal Stage assessment for subjects until Tanner Stage 5 has been reached.

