#### **6.4.4. Week 12 ( $\pm$ 3 days)**

- Perform complete physical examination
- Tanner Pubertal Staging Assessment
- Vital signs, including body weight and height measurements
- Assessment of AEs and concomitant medications
- Pregnancy prevention counseling including partner pregnancy prevention for male participants (Subjects  $\geq$  12 years of age at the discretion of the Investigator based on subject's pubertal status)
- Obtain blood samples for:
  - Hematology
  - Chemistry
  - Coagulation tests
  - HCV RNA
  - Viral sequencing (archive)
  - TSH
  - Single PK
- Obtain urine sample for:
  - $\beta$ -hCG pregnancy test for females of childbearing potential only
- Subject completes quality of life survey: Subject is to review questionnaire with a parent/guardian and write/mark answers directly onto the questionnaire. (GT-2 Subjects only)
- Review medication compliance with subject and/or parent/guardian.

- Dispense study drugs as directed by the IWRS (GT-3 Subjects Only)
- GT-2 Subjects should return all bottles and kits at the Week 12 Visit

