### 9.2.2. Data Handling Conventions

Natural logarithm transformation for key PK parameters, such as  $C_{max}$  and  $AUC_{tau}$ , will be applied for pharmacokinetic analysis.

The PK concentration values below the limit of quantitation (BLQ) will be treated as zero for the determination of summary and order statistics. Individual values that are BLQ will be presented as “BLQ” in the concentration data listing and will be excluded in any calculation of geometric means or ratios. For the presentation of summary and order statistics, if at least 1 subject has a concentration value BLQ for the time point, then the minimum value will be displayed as “BLQ”. If more than 50% of the subjects have a concentration data value BLQ for the time point, then the minimum and median values will be displayed as “BLQ”. If all subjects have concentration data values BLQ for the time point, then all order statistics (minimum, first quartile [Q1], median, third quartile [Q3], maximum) will be displayed as “BLQ”.

Missing data can have an impact upon the interpretation of the trial data. Other than the endpoints discussed below, in general, values for missing data will not be imputed.

For the analysis of post-baseline categorical efficacy endpoints, if a data point is missing and is preceded and followed in time by values that are deemed successes, then the missing data point will be termed a success; otherwise the data point will be termed a failure.

Any subject with missing data due to premature discontinuation of the study medication will be considered a failure at the time points subsequent to the date of discontinuation. If no HCV RNA values are obtained after the last dose of study medication, the subject will be considered a treatment failure for the SVR endpoints.

Where appropriate, safety data for subjects that did not complete the study will be included in summary statistics. For example,

- If a subject received study medication, the subject will be included in a summary of adverse events according to the treatment received; otherwise, if the subject is not dosed then they will be excluded from the summary.

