### **9.5.5. Other Safety Evaluations**

#### **9.5.5.1. Tanner Pubertal Stage Assessment**

Tanner Stages ([Appendix 4](#)) will be summarized by baseline Tanner Stage using frequency and percentage.

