3.5. Missing Data and Outliers

3.5.1. Missing Data

In general, missing data will not be imputed unless methods for handling missing data are specified.

For missing last dosing date of study drug, imputation rules are described in Section 3.7.1. The handling of missing or incomplete dates for adverse event (AE) onset is described in Section 7.1.5.2, and for prior and concomitant medications in Section 7.9.

For analyses of categorical HCV RNA data, missing posttreatment HCV RNA data will have the missing data imputed. Missing on-treatment HCV RNA will have the missing data imputed up to the time of the last dose (for on-treatment displays). If the study day associated with the last dosing date is greater than or equal to the lower bound of a visit window, and the value at the visit is missing, the value will be imputed. If the study day associated with the last dosing date is less than the lower bound of a visit window then the on-treatment value at that visit will remain missing.

If a data point is missing and is preceded and followed in time by values that are “< LLOQ target not detected (TND)”, then the missing data point will be set to “< LLOQ TND”. If a data point is missing and preceded and followed by values that are “< LLOQ detected”, or preceded by “< LLOQ detected” and followed by “< LLOQ TND”, or preceded by “< LLOQ TND” and followed by “< LLOQ detected”, then the missing value will be set to “< LLOQ detected”. In these situations the data point will be termed a bracketed success; otherwise, the data point will be termed a bracketed failure (i.e. \geq LLOQ detected). If a data point is missing and is not bracketed, the missing data point will also be termed a failure (i.e. \geq LLOQ detected) except for SVR24, which will be imputed according to SVR12 status. Success for SVR12 who have no further HCV RNA measurements collected will be counted as a success for SVR24 due to the high correlation between these 2 endpoints.

For the analyses of continuous HCV RNA efficacy data, when and only when a missing HCV RNA value is imputed as < LLOQ TND or < LLOQ detected according to the imputation rule described above, the corresponding continuous value will be imputed to LLOQ - 1 IU/mL. No other imputation will be performed for continuous HCV RNA data.

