In the analysis of the PedsQL™ Pediatric Quality of Life Inventory V4.0 Short Form (SF15) questionnaire, missing data at on-treatment visits and posttreatment follow-up Week 12 (FU-12) visit will not be imputed. Last posttreatment observation carried forward will be used for imputation of missing data at posttreatment follow-up Week 24 visit.

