7.7. Tanner Pubertal Stage Assessment

The Tanner stages will be used to evaluate the onset and progression of pubertal changes. Females will be rated for pubic hair growth and breast development, and males will be rated for pubic hair growth and genitalia development. The Tanner stages (Pubic Hair and Breasts for female; Pubic Hair and Genitalia for male) at EOT, FU-12 and FU-24 visit will be summarized by baseline Tanner stages using frequency count and percentage by sex overall and within each treatment group.

7.8. Pediatric Quality of Life (PedsQL™ SF-15) Questionnaires, Including Neuropsychiatric Examination by Emotional Function Domain

The PedsQL™ Pediatric Quality of Life Inventory V4.0 Short Form (SF15) will be completed at Day 1, EOT (Week 12 for genotype 2 subjects, Week 24 for genotype 3 subjects, or at Early Termination, if applicable), 12-Week Post-Treatment, and 24-Week Post-Treatment visits. Each survey accompanied by the respective parent proxy survey will be administered to the subject and their parent/legal guardian (with the exception of the Toddlers Report which will only be completed by the parent/guardian) for the current age group at the time of survey administration.

The transformed scale scores (0 to 100 scale) at baseline, EOT (Week 12 for genotype 2 subjects, Week 24 for genotype 3 subjects, or at Early Termination, if applicable), 12-Week Post-Treatment, and 24-Week Post-Treatment visits and change from baseline, change from EOT to posttreatment will be presented for each of the 4 domains of the SF-15 (physical functioning, emotional functioning, social functioning, and school functioning), and the Total Score. Scoring of the SF15 scales will be performed as described in Scaling and Scoring of the Pediatric Quality of Life Inventory™ (PedsQL™) by James W. Varni. A Wilcoxon signed rank test will be used to explore within treatment group changes in status from baseline to EOT (Week 12 for genotype 2 subjects, Week 24 for genotype 3 subjects, or at Early Termination, if applicable), and from EOT to each of the posttreatment time points. Results (p-values) will be presented, but should be interpreted with caution as multiple endpoints are being tested, and the study has not been powered to test these exploratory endpoints. Plot of the mean \pm SD of change from baseline in SF15 summary scores will be presented.

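### Protocol 6.6.4 ends Tanner staging at Stage 5 and the SAP carries no Stage 5 forward, so where sites stop staging, the later columns understate cumulative progression to Stage 5

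*Protocol*

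**What the plan says.** Protocol 6.6.4 sets a stopping point for the assessment: "Perform Tanner Pubertal Stage assessment for subjects until Tanner Stage 5 has been reached". It does not say whether one scale or both must be at Stage 5.

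SAP 7.7 rates two scales per subject (pubic hair, plus breasts or genitalia). It says the stages "at EOT, FU-12 and FU-24 visit will be summarized by baseline Tanner stages using frequency count and percentage by sex overall". The same summary is also planned by treatment group. Protocol 9.5.5.1 is shorter: stages "will be summarized by baseline Tanner Stage using frequency and percentage". Neither gives a denominator, a missing-data rule or a convention for Stage 5.

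Both documents default to no imputation. SAP 3.5.1: "In general, missing data will not be imputed unless methods for handling missing data are specified". Protocol 9.2.2: "Other than the endpoints discussed below, in general, values for missing data will not be imputed". The SAP does write a carry-forward rule for PedsQL: "Last posttreatment observation carried forward will be used for imputation of missing data at posttreatment follow-up Week 24 visit". It writes none for Tanner.

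The visit lists do not repeat the stop. Protocol 6.4.4 lists "Tanner Pubertal Staging Assessment" at Week 12 without limiting it to one genotype, and 6.4.6 lists "Tanner Staging Assessment" at Week 24 for GT-3. Protocol 6.4.7, 6.5.2 and 6.5.3, and the tables in protocol Appendix 2 and SAP Appendix 1, also list it with no Stage 5 exemption. The protocol synopsis, under study procedures for the Treatment Phase, places on-treatment staging only at Day 1 and end of treatment.

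**The concern.** Under 6.6.4 a later Tanner value is absent because the subject has reached the top category. The missingness is created by the protocol and is determined by the outcome being tabulated. Subjects who have not reached Stage 5 stay in the later columns, and those who have drop out of them.

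The missing value is not really unknown. Stage V is the last stage in protocol Appendix 4, and stopping there makes sense only if the stage is treated as final.

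Growth and development during and after treatment is a secondary objective, and protocol 9.1.3 names Tanner stage among the secondary safety endpoints. Protocol 1.1 records a concern that ribavirin may reduce growth rates. A table that understates pubertal progression errs in the direction a reader would be watching for.

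**Working it through.** The documents state no figure on this point, so there is nothing to reproduce. The check is a trace through the rules, followed by an illustration.

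**Trace for a subject at Stage 4 on Day 1**

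- *GT-2, first at Stage 5 at Week 12.* Week 12 is EOT, so the subject is counted as Stage 5 there. Staging then stops and FU-12 and FU-24 are missing. GT-2 EOT is correct, because it is the first staging after baseline.
- *GT-3, first at Stage 5 at Week 12, if staged then.* Week 12 is not a tabulated visit for GT-3. Week 24 (EOT), FU-12 and FU-24 are missing, so the subject never appears as Stage 5.
- *GT-3, not staged at Week 12 (synopsis reading).* EOT is the first staging after baseline and is correct. Only FU-12 and FU-24 are affected.
- *Either genotype, first at Stage 5 at FU-12.* Counted there, missing at FU-24.

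**Illustration, baseline Stage 4 row only**

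Assumptions not in the documents: 6.6.4 is followed everywhere, visits are on schedule (12 weeks apart), and the chance of first reaching Stage 5 in each interval is a constant h of 5%, 10% or 20%. At the k-th staging after baseline:

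- cumulative share at Stage 5 = 1 − (1 − h)^k
- share shown among subjects still staged = h
- share shown among all subjects in the baseline row = h(1 − h)^(k−1)

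For example, take 100 GT-2 subjects and h = 10%. EOT shows 10 of 100, FU-12 shows 9 of 90, and FU-24 shows 8.1 of 81. By FU-24 the number who have reached Stage 5 is 10 + 9 + 8.1 = 27.1, but the column shows 10.0% of those still staged, or 8.1% of the full row.

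Results for h = 5 / 10 / 20%, with GT-3 staged at Week 12:

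| Visit | k | Cumulative, % | Shown, still staged, % | Shown, full row, % |
|---|---|---|---|---|
| GT-2 EOT | 1 | 5.0 / 10.0 / 20.0 | 5.0 / 10.0 / 20.0 | 5.0 / 10.0 / 20.0 |
| GT-2 FU-12 | 2 | 9.8 / 19.0 / 36.0 | 5.0 / 10.0 / 20.0 | 4.8 / 9.0 / 16.0 |
| GT-2 FU-24 | 3 | 14.3 / 27.1 / 48.8 | 5.0 / 10.0 / 20.0 | 4.5 / 8.1 / 12.8 |
| GT-3 EOT | 2 | 9.8 / 19.0 / 36.0 | 5.0 / 10.0 / 20.0 | 4.8 / 9.0 / 16.0 |
| GT-3 FU-12 | 3 | 14.3 / 27.1 / 48.8 | 5.0 / 10.0 / 20.0 | 4.5 / 8.1 / 12.8 |
| GT-3 FU-24 | 4 | 18.5 / 34.4 / 59.0 | 5.0 / 10.0 / 20.0 | 4.3 / 7.3 / 10.2 |

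If GT-3 subjects are not staged at Week 12, the GT-3 EOT column shows the full 9.8 / 19.0 / 36.0%. The FU-12 and FU-24 rows are unchanged.

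The direction is the same under both denominators and for every h. With Week 12 staging, the two genotypes are distorted unequally at EOT: at h = 10% both columns show 10.0% of those still staged, although the GT-3 cumulative share is 19.0%.

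**The case against.** The strongest reply is that much of this may not happen. The visit lists and schedule tables ask for staging at each visit with no Stage 5 exemption, so sites working from them would keep staging. That stands: the extent of missing data is unknown. It also means missingness may differ between sites, and a carry-forward rule handles both cases.

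The output is also a descriptive table in a single-arm study. SAP 3 provides by-subject listings, where a recorded Stage 5 stays visible, and height, weight and BMI percentiles (SAP 7.4) and bone age (SAP 7.6) cover growth and development as well. That limits the harm; it does not make the later columns right.

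A reader might infer more than the documents support:

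- *That SAP 7.7 calls for observed data only.* It does not say so. That reading comes from the general default in SAP 3.5.1.
- *That subjects who complete puberty vanish from the tables.* A subject first at Stage 5 at a tabulated visit is counted there and lost only afterwards. The exception is a GT-3 subject first at Stage 5 at an untabulated Week 12 staging.
- *That an empty baseline Stage 5 row understates progression.* Those subjects cannot progress, and the table is split by baseline stage.
- *That the table will produce a false safety signal of a known size.* No baseline stage distribution or progression rate is given, no test is applied, and there is no concurrent control group.

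**Conclusion.** The concern holds in a limited form. Where 6.6.4 is followed and the no-imputation default is applied, cumulative progression to Stage 5 is understated at FU-12 and FU-24 for both genotypes. It is understated at GT-3 EOT only if Week 12 staging is done, on which protocol 6.4.4 and Appendix 2 disagree with the synopsis. GT-2 EOT is unaffected.

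The direction follows from the rules alone. The size does not: it depends on how many sites stop staging, how many subjects start below Stage 5, and how fast they progress. The percentages above are illustrations for one baseline row under an assumed rate. This is a minor reporting gap in a secondary safety table, with no bearing on sample size, power or alpha, but it is predictable and cheap to remove.

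**What to change.** In SAP 7.7:

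- Once Stage 5 is recorded for a scale (pubic hair; breasts or genitalia), carry it forward for that scale to all later tabulated visits.
- Base percentages on subjects with an observed or carried-forward stage at the visit.
- Define EOT for Tanner by genotype, as SAP 7.8 already does for PedsQL.

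In the protocol, reconcile 6.6.4 with the visit lists, the Appendix 2 tables and the synopsis. State whether one or both scales must be at Stage 5 before staging stops. This matters because carry-forward cannot recover a scale that was still below Stage 5 when staging ended.

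The SAP part costs one derivation step and a few carried-forward values in a descriptive table, and uses data already collected. The protocol part is a modification that needs approval under protocol 10.2.1. If it results in staging continuing until both scales are at Stage 5, some subjects would have extra assessments, at visits already scheduled.
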